9.3 Primary Endpoints

The primary objective of this phase I/II study is to evaluate the safety and activity profile of h-ATG/CsA/eltrombopag in treatment naïve SAA.

- The primary safety endpoint will be toxicity profile in the 6 months following h-ATG/CsA/eltrombopag.
- The primary efficacy endpoint is CR rate at 6 months (see section 7 for CR definition).

Subjects who drop out, who have failed to respond and opt for alternative therapy (e.g. bone marrow

transplant), or who require eltrombopag to be restarted (cohort 2 only) before the 6-month evaluation will be counted as non-responders.

9.4 Secondary Endpoints

Secondary endpoints will also be evaluated for the study to include: (a) hematological response at 3 and 12 months and yearly thereafter; (b) relapse (c) clonal evolution to PNH, clonal chromosomal population in bone marrow, myelodysplasia by morphology, or acute leukemia; (d) survival; (e) health-related quality of life; (f) hematological response of relapse subjects that re-start treatment; and (g) affects of a 2.0mg/kg/day CsA dose starting month 6 for 18 months until month 24 on the rate of relapse of subjects deemed responders at month 6.

Subjects will be followed up to 60 months so that long-term disease-free and overall survival can be estimated. Response and toxicity comparisons will also be made with the results obtained from prior NHLBI studies: the h-ATG/CsA protocol (90-H-0146); the h-ATG/CsA vs. Cytoxan/CsA protocol (97-H-0117); the h-ATG/CsA/MMF protocol (00-H-0032); the h-ATG/CsA/Rapamune protocol (03-H-0193); the 3-arm randomized study (06-H-0034) and the r-ATG vs. alemtuzumab (03-H-0249) trials.

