2.9.1 Justification for adding Cohort 2 (August 2013)

In this study, we are observing more rapid hematologic improvement than observed with immunosuppression alone. The overall response rate of 84% (11/13) at 6 months, with 100% of these responses observed by 3 months, is also higher than in historical data. As subjects currently receive eltrombopag for 6 months but blood counts have improved by 3 months, it is possible that administration of eltrombopag may only be necessary for the shorter duration, lowering risk, cost, and inconvenience. In particular, limiting exposure to eltrombopag may reduce the risk of cytogenetic evolution. Further, in the event of relapse, expected with discontinuation of treatment, we can now not distinguish whether cyclosporine or eltrombopag is responsible, as both are administered concurrently. Therefore, we propose to treat another cohort (cohort 2) of 31 subjects, with no change to this protocol other than a reduction in eltrombopag administration from 6 to 3 months. The study objectives, primary and secondary endpoints, statistics – sample size, stopping rules, eligibility, monitoring and ancillary studies will remain unchanged. Responses at 3 months can be assessed for the two cohorts, providing a confirmation cohort for our early results, whereas new information will be provided by comparison of long-term outcomes between the two cohorts. These data can be used to inform design of a future randomized, multicenter phase III trial. Note amendment 17 was submitted on October 23, 2014 to increase Cohort 2 sample size to 33 subjects in order to allow subjects to be enrolled and treated while amendment 16 to add Cohort 3 was being reviewed. Note, only 31 subjects were enrolled into Cohort 2 because the Cohort 3 amendment was approved prior to needing to enroll the 2 additional subjects into Cohort 2.

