2.9.2 Justification for adding Cohort 3 (September 2014)

As of September 15, 2014, 57 subjects have been enrolled on the protocol (31/31 in cohort 1, and 26/31 in cohort 2) and the combination of cyclosporine and eltrombopag has been safe and well tolerated. Higher overall response rates with eltrombopag compared to immunosuppression alone are a consistent observation from both the first and second cohort. Most subjects respond within 2-3 weeks of the first dose of eltrombopag alleviating the transfusion burden sooner than our historical cohort. In cohort 2, where eltrombopag is discontinued at 3 months in all subjects, all subjects have either maintained or normalized their blood counts between 3 and 6 months. In cohort 1 and cohort 2 eltrombopag was implemented to begin on Day 14 to avoid any potential hepatotoxicity from the combination of cyclosporine and h-ATG. However, now that we have ample data indicating the combination of cyclosporine and eltrombopag is safe, the earlier initiation of eltrombopag on Day 1 in combination with hATG should be tested in a third cohort. Therefore, we propose to treat another cohort (cohort 3) of 31 subjects, where eltrombopag will be administered without delay, starting Day 1, with the intention of accelerating hematologic recovery. Eltrombopag will be discontinued at the 6-month landmark visit.

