3. STUDY DESIGN

[figure not shown]
This study is designed as a non-randomized, pilot phase I/II study in which 182 subjects with severe aplastic anemia who have not received prior definitive immunosuppressive therapy will be treated with a standard regimen of h-ATG/CsA, combined with eltrombopag as experimental therapy. The first 31 subjects will be enrolled to cohort 1. Then up to 33 subjects will be enrolled to cohort 2 while up to 31 subjects will be enrolled in cohort 3. Subjects enrolled to cohort 1 will receive eltrombopag for 6 months whereas subjects enrolled to cohort 2 will receive eltrombopag for 3 months. Subjects enrolled in cohort 3 will initiate h-ATG, CsA and eltrombopag on Day 1. The primary clinical endpoint of this study is the quality of hematologic response at 6 months. In cohorts 1 and 2 eltrombopag will be initiated on day 14 to avoid overlap with the known transient hepatotoxicities associated with ATG and cyclosporine. Cohort 3 will initiate h-ATG, CsA, and eltrombopag on Day 1 if there are no significant hepatotoxicities seen in cohorts 1 and 2. Patient-reported outcome questionnaires (Appendix E) will be collected initially when the subject enrolls on-study (pre-ATG/CSA), pre-eltrombopag, at 3 and 6 months, and annually for 5 years.

Up to an additional 87 subjects may be enrolled into the Extension Cohort in order to allow subjects to be enrolled and treated while a new SAA treatment naïve protocol is developed and approved. In addition, 25 subjects will be enrolled for Laboratory Exploratory Cohort. The treatment schedule for both the Extension & Laboratory cohorts will be the same as Cohort 3.

Protocol Design for Cohort 1

[figure not shown]

Protocol Design for Cohort 2 added August 2013

[figure not shown]

*Cohort 2 will continue CsA administration month 6 to month 24 at 2.0mg/kg per amendment number 15

Protocol Design for Cohort 3 added September 2014

Protocol Design for Extension Cohort and Laboratory Exploratory Cohort

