At the 6-month landmark visit, responders will have the CsA dose reduced to 2.0mg/kg/day administered orally at a fixed dose through the 24 month timepoint. Previous anecdotal experience suggested that a gradual taper of CsA may avoid relapse, but when we adopted this strategy prospectively in our clinical trials (03-H-0193 and 06-H-0034) the rate of relapse was unchanged (Scheinberg, Rios, et al. AJH 2014⁶⁷). However, time to relapse was delayed by 1 year with the longer course of CsA and may be dose-dependent. The CsA dose at the time of relapse during the taper phase was at a median of 1.32 (range: 0.52-4.18) mg/kg/day and a mean of 1.8 mg/kg/day. This suggests that a CsA dose level above these levels might preclude relapse and improve tolerability of chronic maintenance. For remaining subjects due for the 6 month timepoint on cohort 2 we will prolong administration of cyclosporine beyond 6 months. CsA will continue to be administered from Day 1 to 6 months, but from 6 months to 2 years CsA will be administered at a lower fixed daily dose (2 mg/kg/day) in an attempt to improve relapse, a secondary endpoint, among responders in the study.

Medication dosing errors, dose delays or dosing interruptions:

Interruptions such as delays in request for medication refills or medication errors by subjects will be recorded in the medical record.

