9.2 Statistical Methods

For each cohort, the planned analyses will include descriptive statistics on the proportions of responses (% subjects with partial or complete response), cumulative incidence of response with death considered to be a competing risk and the time to complete response. The response probabilities, including complete response probability and partial response probability, will be estimated using the sample proportions, and their inferences, including confidence intervals and hypotheses testing, will be evaluated using Binomial distributions. Survival analysis will include methods based on Kaplan-Meier estimates and Cox regression. Although we have a small sample size, if it is appropriate, we will consider additional analyses for the primary and secondary endpoints using the analysis of variance, multiple regression and logistic regression models. Graphical tools will be used to display the appropriate estimates (i.e. estimated proportions and Kaplan-Meier curves) and their corresponding 95% confidence intervals.

Results for each cohort will be compared separately to the historical data from the large numbers of patients treated at the NIH previously with either a single or repeat course of immunosuppression from prior NHLBI studies: the h-ATG/CsA protocol (90-H-0146); the h-ATG/CsA vs. Cytoxin/CsA protocol (97-H-0117); the h-ATG/CsA/MMF protocol (00-H-0032); the h-ATG/CsA/Rapamune protocol (03-H-0193); the r-ATG vs. alemtuzumab protocol (03-H-0249); and h-ATG/CsA vs. r-ATG/CsA protocol (06-H-0034). More specifically, results from the current trial will be compared to our large historical experience with a horse ATG based regimen in nearly 400 patients (from the aforementioned studies) of a hematologic response rate of 60-70%, a complete response rate of 10-15%, a relapse rate of 30-40%, a clonal evolution rate (any clonal abnormality) of 15-20%, and a high risk evolution rate (to monosomy 7, high risk MDS, leukemia, or complex cytogenetics) of 10-15%.

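### Secondary endpoint 9.4(g) is worded as an effect of low-dose cyclosporine on relapse, but the only comparison the plan specifies, against history without eltrombopag, cannot support a statement about cyclosporine

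*Combined protocol and SAP*

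**What the plan says.** Section 9.4 lists as item (g) "affects of a 2.0mg/kg/day CsA dose starting month 6 for 18 months until month 24 on the rate of relapse" among subjects who are responders at month 6. It gives no comparator, estimand or method for this item.

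The schedules come from four places. For Cohort 3, section 2.9.2 states "Eltrombopag will be discontinued at the 6-month landmark visit". Section 5.2 states "At the 6-month landmark visit, responders will have the CsA dose reduced to 2.0mg/kg/day", to be held at that dose to month 24. For the later cohorts, section 3 states "The treatment schedule for both the Extension & Laboratory cohorts will be the same as Cohort 3". For Cohort 1, section 5.7 has eltrombopag and CsA both ending at month 6.

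On comparison, section 9.2 states "Results for each cohort will be compared separately to the historical data" from earlier institutional protocols, and gives that history "a relapse rate of 30-40" percent. None of the listed protocols includes eltrombopag. Section 5.2 adds that two of them (03-H-0193 and 06-H-0034) used a prolonged CsA taper, under which "the rate of relapse was unchanged" although relapse came about a year later.

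Two passages in section 9.1 are milder. One introduces the same objective as a relapse rate between months 6 and 24 on low-dose CsA. The other limits the Extension Cohort to descriptive statistics.

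**The concern.** The plan has already recognised this kind of confounding. In section 2.9.1, where both drugs end together, it says of relapse that "we can now not distinguish whether cyclosporine or eltrombopag is responsible, as both are administered concurrently", and it gives this as one reason for Cohort 2. Cohort 3 and the Extension Cohort bring much of the problem back, because both drugs change at one visit.

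If the plan is followed as written, relapse below 30-40% could be credited to low-dose CsA when it came from having received eltrombopag. Relapse at or above that range could be blamed on the CsA dose when it came from stopping eltrombopag. Either error would feed a conclusion about maintenance CsA after this regimen. Relapse prevention is also a stated aim of adding eltrombopag (Precis), so an eltrombopag contribution cannot be set aside.

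**Working it through.** The documents give no sample size, power or effect size for (g), so there is no planned figure to reproduce. The check compares schedules and then works an illustration.

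**1. What differs between the groups**

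| Group | Eltrombopag | CsA after month 6 | n |
|---|---|---|---|
| History (9.2) | never | mixed, with a prolonged taper in two protocols (5.2) | nearly 400 |
| Cohort 1 | day 14 to month 6 | stopped (5.7) | 31 |
| Cohort 2, earlier subjects | day 14 to month 3 | stopped (5.7) | part of 31 |
| Cohort 2, later subjects | day 14 to month 3 | 2 mg/kg/day (3, 5.2) | rest of 31 |
| Cohort 3 | day 1 to month 6 | 2 mg/kg/day | 31 |
| Extension Cohort | as Cohort 3 | as Cohort 3 | 87 |

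Against history, Cohort 3 and the Extension Cohort differ in eltrombopag exposure, eltrombopag withdrawal and CsA after month 6. Against Cohort 1, the month-6 eltrombopag stop is common to both sides. What remains is CsA, the eltrombopag start day and the calendar period.

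**2. Why history cannot isolate CsA**

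As an illustrative assumption, let observed relapse = historical rate × RR(CsA) × RR(E), where RR(E) covers eltrombopag exposure and withdrawal together. With a historical rate of 35%:

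- 0.35 × 1.0 × 1.0 = 35%
- 0.35 × 0.75 × 1.33 = 34.9%
- 0.35 × 0.5 × 2.0 = 35%

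The same observation fits a CsA effect anywhere from none to a halving. Conversely, a true halving by CsA would show as 17.5%, 23.3% or 35% for RR(E) of 1, 1.33 or 2. A larger sample does not resolve this.

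**3. What the in-trial contrast could deliver**

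Assume 85% respond at month 6 (section 2.9.1 reports 84%, 11 of 13). Responders are 0.85 × 31 ≈ 26 in Cohort 1 and 0.85 × 118 ≈ 100 in Cohort 3 plus Extension. For assumed relapse of 35% versus 20%, treated as simple proportions:

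half-width = 1.96 × √(0.35 × 0.65/26 + 0.20 × 0.80/100) = 1.96 × √(0.00875 + 0.00160) = 0.199

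The difference is 15 points with a 95% interval of about −5 to +35. Varying the response rate:

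- 65% (20 vs 77): 1.96 × √(0.2275/20 + 0.16/77) = 0.227
- 90% (28 vs 106): 1.96 × √(0.2275/28 + 0.16/106) = 0.192

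At 84% response, power to detect a halving (two-sided 0.05) from 30%, 35% or 40% is 0.43, 0.50 or 0.56 with 26 vs 99 responders. With Cohort 3 alone (26 vs 26) it is 0.25, 0.30 or 0.35. This supports reporting an estimate with an interval and no test.

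**The case against.** **The objective may be purely descriptive.** Section 9.1 words it as a rate, and the Extension Cohort is limited to descriptive statistics. This stands to the extent that (g) can be answered as a rate. It does not remove the effect wording in 9.4 or the historical comparison in 9.2.

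**In-trial controls exist.** Section 2.9.1 foresees comparing long-term outcomes of Cohorts 1 and 2, and 9.2 allows further regression analyses. That is true, but no section assigns these groups to (g). The 2.9.1 comparison concerns eltrombopag duration and was written before the CsA change. A reader might infer that the trial cannot inform the CsA question at all. The documents do not support that: the failure belongs to the planned historical comparison.

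**Section 2.9.1 is not the same case.** It concerns two drugs that both stop, whereas in Cohort 3 CsA is reduced. This stands, so the parallel is partial. The coincidence in time remains.

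**The Cohort 1 contrast has its own biases.** This stands, for five reasons:

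- Section 5.2 says CsA was prolonged because relapse after month 6 was running above expectation in data to September 2014. By section 2.9.2 only Cohorts 1 and 2 had then been enrolled. If their excess was partly chance, regression to the mean would favour low-dose CsA.
- Calendar period and eltrombopag start (day 14 versus day 1) differ.
- Section 7 dates relapse by resuming CsA, or by needing more of it if already on the low dose. The event is therefore not recorded identically in the two groups.
- Longer CsA has previously delayed relapse without changing its rate (5.2), so a month-24 result alone could present delay as prevention.
- Section 5.7 says CsA stops at month 6 in Cohorts 1 and 2, whereas sections 3 and 5.2 continue it in Cohort 2.

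**The Laboratory Exploratory Cohort.** A reader might add these 25 subjects, who follow the same schedule, to reach 143. Section 2.9.4 keeps them out of the Extension Cohort's secondary-endpoint analysis, so the relevant count is 118.

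**Conclusion.** The concern holds for the planned analysis. For the 118 subjects of Cohort 3 and the Extension Cohort, the comparison in 9.2 cannot separate CsA maintenance from eltrombopag exposure and withdrawal, so it cannot carry the effect wording of 9.4(g). This conclusion rests on the documented schedules; the relative risks above only illustrate it.

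A better contrast is available from data already being collected, but it is modest. It is non-randomised, with a 95% interval of about ±20 points under 85% response and relapse of 35% versus 20% (±19 to ±23 for response of 90% down to 65%). It also assumes that Cohort 1 stopped CsA at month 6 as section 5.7 states. It would improve the interpretation of (g) without settling the question. The issue concerns one secondary endpoint and leaves the primary analysis untouched.

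**What to change.** 1. Reword 9.4(g) to agree with section 9.1: relapse rate from month 6 to month 24 in month-6 responders on low-dose CsA. In 9.2, describe the historical comparison for Cohort 3 and the Extension Cohort as relapse after eltrombopag stop plus CsA reduction, not as a CsA effect.
2. Add to 9.2 the cumulative incidence of relapse from the month-6 landmark in month-6 responders of Cohort 3 plus Extension versus Cohort 1. Give the difference with a 95% confidence interval and no test. Report it at month 24 and at a later time within the 5-year follow-up, fixed before analysis.
3. As support, compare Cohort 2 responders with and without continued CsA, once section 5.7 has been reconciled with sections 3 and 5.2.
4. State the limits beside the result: non-randomised groups, different calendar periods and eltrombopag start days, controls whose relapses prompted the CsA change, relapse dated by resuming or raising CsA, and the wide interval.

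The cost is a wording change and one additional analysis of data already being collected. Treatment, visits and sample size do not change. The drawback is an imprecise observational estimate that must be reported with its caveats.

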9.5 Stopping Rules

Evolution to clonal hematopoiesis will be monitored and documented in this study. Currently, there are no standards to determine if evolution to clonal hematopoiesis with respect to this study is a serious adverse event or treatment related serious adverse event. Therefore, evolution to clonal hematopoiesis will not be included in stopping rules. Currently, none of the active SAA NHLBI Hematology Branch treatment protocols includes evolution to clonal hematopoiesis as a stopping rule, including all protocols administering eltrombopag.

Cohorts 1, 2 & 3

The study will be monitored to ensure that the occurrence of a specified set of treatment related serious adverse events (TRSAEs) within 6 months of treatment in the trial does not substantially exceed an anticipated rate. The following TRSAEs will be monitored for early stopping of the study:

- Death considered to be probably or definitely related to eltrombopag.
- Any grade IV toxicity considered to be probably or definitely related to eltrombopag.
- Grade IV thrombosis/embolism

The study will be monitored using the stopping rules as outlined below for early stopping if the number of subjects in the study who have developed one or more of the above specified TRSAEs is over a pre-specified threshold value. TRSAEs are those attributed as definitely or probably related to eltrombopag. [name] will serve as the independent monitor who reviews the attribution of TRSAEs.

From our experience using this agent in other clinical settings, we anticipate the rate of developing at least one of the above specified TRSAEs for this patient population to be 20% or less. Following Geller et al. 2004, (Nancy L. Geller, Dean Follmann, Eric S. Leifer, and Shelly L. Carter “Design of Early Trials in Stem Cell Transplantation: A Hybrid Frequentist-Bayesian Approach” Chapter 2, pp 41-52, Advances in Clinical Trial Biostatistics, 2004, Marcel Dekker: New York), our stopping rule is determined by a Bayesian approach. The stopping boundary for the study is reached if the Bayesian posterior probability that the true probability of developing one or more of the above specified TRSAEs exceeds this benchmark rate of 20% is at least 90%. We take our prior distribution to be a beta distribution with the sum of the two beta

parameters to be 3, i.e. the parameters of the beta prior distribution are 0.60 and 2.40. Since we have seen in the past that the first few subjects to be accrued are possibly sicker than the rest of the subjects in the sample, we will start safety monitoring the study when 3 or more subjects have developed specified TRSAEs. The following tables summarize the threshold numbers for stopping the study:

Number of Tx naïve SAA subjects enrolled	Stop if the number of Tx naïve SAA subjects who develop any of the specified TRSAEs reaches:
≤ 6	3
≤ 9	4
≤ 13	5
≤ 17	6
≤ 21	7
≤ 25	8
≤ 29	9
≤ 31	10
≤ 37	11
≤ 41	12
≤ 45	13
≤ 49	14
≤ 54	15

For the stopping rule we generated a study with 25 independent Bernoulli trials, each had a probability p for having the above TRSAE and $q=1-p$ for not having such TRSAE and compared the TRSAE outcomes with the above stopping boundary to determine whether the study was stopped. We repeated the simulation 100,000 times and computed the proportion of stopped studies (i.e. “number of stopped studies”/100,000), which were stopped using the above stopping rule. The following table summarizes the proportions of stopped studies under a number of scenarios for p :

Probability of “Monitored” TRSAE= p	5%	10%	15%	20%	25%	40%
Proportion of stopped studies	0.27%	2.45%	9.19%	22.57%	41.44%	89.81%
Average number of Tx naïve SAA subjects	24.95	24.58	23.59	21.78	19.30	11.02
Average number of Tx naïve SAA with a specified TRSAE	1.25	2.47	3.53	4.35	4.83	4.41

These results suggest that the above stopping rules have a low probability of stopping a study when the proportion of the corresponding specified TRSAE is below the benchmark value of 20%, and the probability of stopping a study is high when the true proportion of the above specified TRSAE exceeds this benchmark value. Based on these results, we believe that our Bayesian stopping rules have satisfactory statistical properties.

Extension Cohort

Following Amendment FF, we updated the TRSAE stopping rule for this expanded cohort of N=87 patients (55 patients in the original cohort, 32 additional patients) the TRSAE stopping rule is updated using the

same Bayesian approach (Geller et al., 2004) with the same assumptions. Specifically, the assumptions are:

- a) The rate of developing one or more of the specified TRSAEs is 20% or less.
- b) The stopping boundary is reached if the Bayesian posterior probability that the true probability of developing one or more of the specified TRSAEs exceeds this benchmark rate of 20% is at least 90%.
- c) The prior distribution is a beta distribution with the sum of the two beta parameters to be 3, i.e. the parameters of the beta prior distribution are 0.60 and 2.40.
- d) The safety monitoring starts when 3 or more subjects have developed the specified TRSAEs.

The following tables summarize the threshold numbers for stopping the study:

Number of Tx naïve SAA subjects enrolled	Stop if the number of Tx naïve SAA subjects who develop any of the specified TRSAEs reaches:
≤ 6	3
≤ 9	4
≤ 13	5
≤ 17	6
≤ 20	7
≤ 24	8
≤ 29	9
≤ 33	10
≤ 37	11
≤ 41	12
≤ 45	13
≤ 49	14
≤ 54	15
≤ 58	16
≤ 62	17
≤ 66	18
≤ 71	19
≤ 75	20
≤ 80	21
≤ 84	22
≤ 87	23

We performed a simulation study to verify the appropriateness of this stopping rule. In each simulation run, we generated a study with 87 independent Bernoulli trials, each had a probability p for having the above TRSAE and $q=1-p$ for not having such TRSAE and compared the TRSAE outcomes with the above stopping boundary to determine whether the study was stopped. We repeated the simulation 100,000 times and computed the proportion of stopped studies (i.e. “number of stopped studies”/100,000), which were stopped using the above stopping rule. The following table summarizes the proportions of stopped studies under several different scenarios for the true value of p :

Probability of “Monitored” TRSAE= p	5%	10%	15%	20%	25%	40%

Proportion of stopped studies	0.27%	2.38%	10.35%	32.83%	66.73%	99.90%
Average number of Tx naive SAA subjects	86.78	86.13	79.57	66.31	47.15	12.58
Average number of Tx naive SAA with a specified TRSAE	4.34	8.50	11.93	13.27	11.79	5.04

These results suggest that the above stopping rule has a low probability of stopping a study when the proportion of the corresponding specified TRSAE is below the benchmark value of 20%, and the probability of stopping a study is high when the true proportion of the above specified TRSAE exceeds this benchmark value. Based on these results, we believe that our Bayesian stopping rule has satisfactory statistical properties.

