The current pilot study design has a cohort of 31 subjects receiving eltrombopag starting day 14 and ending at the 6 month time point (cohort 1). With **amendment (8), submitted on August 22, 2013**, once accrual to cohort 1 has been completed without reaching any study stopping rules we propose to treat another cohort (cohort 2) of 33 subjects whereby they would be treated with the same regimen except that they would receive a reduction in exposure to eltrombopag from 6 to 3 months. The primary and secondary endpoints, objectives, eligibility, statistics, including sample size and stopping rules, monitoring and ancillary studies apply the same way for cohort 2 as for cohort 1. With amendment 16, submitted on October 2, 2014, once accrual to cohort 2 has been completed without reaching any stopping rules we propose to treat another cohort (cohort 3) of 31 subjects whereby they would be treated with the same regimen except that they would start h-ATG, CsA, and eltrombopag on Day 1. Eltrombopag will be administered up to the 6-month landmark visit. The primary and secondary endpoints, objectives, eligibility, statistics, including sample size and stopping rules, monitoring and ancillary studies apply the same way for cohort 3 as for cohorts 1 and 2 with the exception of one additional secondary objective (relapse rate between month 6 to month 24 when receiving low CsA during this time period).

	Sample size (n)	Eltrombopag	Primary Efficacy Endpoint	Statistical Design
Cohort 1	31	D 14 – 6 months	CR rate at 6 months	Simon Two-Stage
Cohort 2	33	D14 – 3 months	CR rate at 6 months	Simon Two-Stage
Cohort 3	31	D1 – 6 months	CR rate at 6 months	Simon Two-Stage

Starting with Amendment V, an extension cohort was added of 55 subjects in order to have data to improve precision of exploratory analysis of secondary endpoints, and to obtain more pharmacokinetic data on the

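### Section 9.5 says the TRSAE rule is likely to stop whenever the true rate exceeds 20%, but this holds only for large excesses: at a true 25% it stops 41% (n=25), 45% (n=31) or 67% (n=87) of the time

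*Combined protocol and SAP*

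**What the plan says.** Section 9.5 monitors deaths and grade IV toxicities probably or definitely related to eltrombopag, and grade IV thrombosis or embolism, within 6 months of treatment. Its stated purpose is to make sure that their rate does not exceed the anticipated rate by a substantial amount. The benchmark is given as "we anticipate the rate of developing at least one of the above specified TRSAEs for this patient population to be 20% or less". The boundary is reached when the posterior probability of a rate above 20% is at least 90%. For the prior, "the parameters of the beta prior distribution are 0.60 and 2.40", and "we will start safety monitoring the study when 3 or more subjects have developed specified TRSAEs".

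For Cohorts 1 to 3 the operating characteristics come from a simulation in which "we generated a study with 25 independent Bernoulli trials". The table has columns for true rates of 5, 10, 15, 20, 25 and 40%. The text below it concludes that "the probability of stopping a study is high when the true proportion of the above specified TRSAE exceeds this benchmark value" and that the properties are satisfactory. The Extension Cohort has its own boundary and an 87-subject simulation, followed by the same conclusion.

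Section 9.1 applies the same stopping rules in each cohort and places the cohorts in sequence: "once accrual to cohort 1 has been completed without reaching any study stopping rules we propose to treat another cohort", and later "once accrual to cohort 2 has been completed without reaching any stopping rules we propose to treat another cohort".

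**The concern.** The conclusion carries no qualifier, so it covers every rate above 20%. The nearest such rate in the Cohorts 1 to 3 table is 25%, where the rule stops fewer than half of the simulated studies. The next column is 40%, so the range in which the rule moves from unlikely to likely to stop is not shown. The simulated size of 25 is also not the size of any cohort: Cohorts 1 and 3 have 31 subjects, and Cohort 2 has a ceiling of 33 with 31 enrolled.

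Safety is part of the primary objective in section 9.3. Someone who relies on the sentence rather than the table would credit the rule with protection against moderate excesses that it does not have. They could then take an unstopped cohort as better evidence about the TRSAE rate than it is.

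**Working it through.** **Inputs, all from section 9.5 unless noted.** Benchmark 20%; stop when the posterior P(rate > 20%) is at least 0.90; prior Beta(0.60, 2.40); printed thresholds b(n) for n subjects enrolled (3 events at n ≤ 6, up to 10 at n ≤ 31 for Cohorts 1 to 3, and up to 23 at n ≤ 87 for the Extension Cohort). Cohort size 31 is from section 9.1. Outcomes are treated as known at once, as in the plan's simulation.

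**Method.** Let f_n(k) be the probability that the study has not stopped after n subjects and has k subjects with a TRSAE. With true rate p,

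f_n(k) = (1 − p) · f_{n−1}(k) + p · f_{n−1}(k − 1), kept only for k < b(n).

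The stopping probability is 1 − Σ_k f_N(k). This is the exact counterpart of the plan's 100,000-run simulation.

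**Step 1: reproduce the plan's figures (probability of stopping, %).**

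| True rate | n=25 printed | n=25 exact | n=87 printed | n=87 exact |
|---|---|---|---|---|
| 5% | 0.27 | 0.27 | 0.27 | 0.26 |
| 10% | 2.45 | 2.41 | 2.38 | 2.44 |
| 15% | 9.19 | 9.14 | 10.35 | 10.56 |
| 20% | 22.57 | 22.52 | 32.83 | 32.86 |
| 25% | 41.44 | 41.41 | 66.73 | 66.92 |
| 40% | 89.81 | 89.69 | 99.90 | 99.91 |

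Agreement is within about 0.2 percentage points throughout. The printed stopping probabilities are sound; the issue is the sentence drawn from them.

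**Step 2: add the actual cohort size and the missing rates (exact, %).**

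| True rate | n=25 | n=31 | n=87 |
|---|---|---|---|
| 20% | 22.5 | 24.1 | 32.9 |
| 25% | 41.4 | 44.9 | 66.9 |
| 30% | 61.5 | 66.3 | 90.9 |
| 40% | 89.7 | 93.0 | 99.9 |

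At a true 25% the rule therefore fails to stop with probability 100 − 41.44 = 58.6% (n=25, printed), 100 − 44.9 = 55.1% (n=31) and 100 − 66.73 = 33.3% (n=87, printed).

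**Step 3: find the rate at which stopping becomes likely.** Taking 80% as a conventional marker (the plan sets none) and solving for p gives 35.6% (n=25), 33.9% (n=31) and 27.2% (n=87).

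**Step 4: what an unstopped cohort can contain.** With x events in n subjects the plan's model gives Beta(0.6 + x, 2.4 + n − x).

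- Largest unstopped result at n=31: 9 events (29%). Posterior Beta(9.6, 24.4); P(rate > 20%) = 0.86; one-sided 95% upper credible limit 41.5%.
- Largest unstopped result at n=87: 22 events (25%). Posterior Beta(22.6, 67.4); P(rate > 20%) = 0.87; one-sided 95% upper credible limit 32.9%.

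These are the extremes. By the same recursion, finishing unstopped with exactly 9 of 31 has probability 3.5% at a true 25% and 4.0% at a true 30%.

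**The case against.** The strongest reply is that the rule does what it was built for. Its stated aim is a substantial excess over the benchmark, and at 40% it stops about 90% of studies with 25 subjects and nearly all with 87. No rule on 25 to 31 subjects separates 20% from 25% well, and this one already stops 22.57% of the time at exactly 20%. The figures are printed directly above the sentence. All of this stands, and it is why the boundary need not change. It does not rescue the sentence: the concluding text drops the idea of a substantial excess, never says how large an excess counts, and shows nothing between 25% and 40%.

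A reader might go further and infer that the plan treats not stopping as proof of an acceptable TRSAE rate and opens the next cohort on that basis alone. The documents do not support this. Section 9.1 gives a sequence, and section 9.5 does not mention opening cohorts. The reasons for adding Cohorts 2 and 3 in sections 2.9.1 and 2.9.2 are observed response and tolerability data. The cohorts came through amendments, which the IRB approves. The DSMB reviews the protocol every 6 to 12 months and may recommend termination (section 10.1), and the Cohort 3 schedule also required no significant hepatotoxicity in Cohorts 1 and 2 (section 3). None of these safeguards puts a number on the TRSAE rate, but they mean that an outcome such as 9 of 31 would not lead automatically to a new cohort.

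It is also fair that accrual to Cohorts 1 to 3 is over, so the practical effect now lies in how the safety results are described and in the Extension Cohort text.

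**Conclusion.** The point holds as a mismatch between a stated operating property and the plan's own figures. Stopping is likely for large excesses over 20%, from about 34% to 36% in cohorts of 31 or 25 and about 27% in the Extension Cohort. For moderate excesses in Cohorts 1 to 3 it is not: 45% at a true 25% and 66% at a true 30% with 31 subjects. It follows that not reaching the boundary does not by itself show a rate of 20% or less. No claim is made that the rule is mis-specified, that a cohort was opened wrongly, or that an upper limit must be an acceptance criterion; the last would be a design preference, since the primary safety endpoint is a descriptive toxicity profile.

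The figures assume independent outcomes with a common rate, known immediately, and the printed boundary. Three printed thresholds for Cohorts 1 to 3 extend one subject further than the stated posterior rule gives (7 events to n = 21, 8 to 25 and 9 to 29, against 20, 24 and 28). Applying the stated rule exactly lowers stopping at 25% for n=25 from 41.4% to 38.8%, so the conclusion does not depend on this. The 80% marker is conventional, not the plan's.

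**What to change.** 1. In both places in section 9.5, replace the sentence with the actual figures. Suggested wording: at a true TRSAE rate of 25% the rule stops with probability 41% (n=25), 45% (n=31) and 67% (n=87); at 30%, 62%, 66% and 91%; 80% is reached at about 36%, 34% and 27%. Add the 30% column and the actual cohort size of 31 to the tables.
2. Limit the claim of satisfactory properties to excesses of that size.
3. State that not reaching the boundary does not by itself show a TRSAE rate of 20% or less.
4. After each cohort completes its 6-month window, report to the DSMB and in the results the TRSAE rate, P(rate > 20%) and the 95% upper credible limit from the same Beta(0.6, 2.4) model. Label the limit as one-sided and the whole as a descriptive summary.

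The boundary and the cohort sequence stay as they are, and no new acceptance threshold is imposed. The cost is a text change and one posterior calculation per cohort from data already collected, with no extra subjects or procedures. The downside is that the stated protection will look less favourable.
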